### 5.5 Strategies for Recruitment and Retention

The recruitment process planned for this study will include any of the following scenarios:

- An individual voluntarily schedules an appointment at the physician's office (that in the context of this study also functions as the investigator's test site) relating to the treatment of photoaging.
- The study population may also be drawn from the investigator's existing database of subjects who have expressed an interest in treatment of photoaging.
- During the visit, if the physician perceives the subject may satisfy the study qualification criteria, the physician will present to the subject the option of being a subject in the study.
- If the subject is interested in possibly taking part in the study, the physician now in the role of study investigator will personally review the informed consent form with the individual and answer any questions. The individual may sign the informed consent form at that visit or he or she may think about it for a while and sign the informed consent form later. No timeline may be set for the subject to sign the consent form. Furthermore, the subject can refuse to participate in the study.
- An individual who decides to sign the consent form and proceed with participation in the study will receive a subject ID and proceed to the study qualification phase.
- Treatment will include a screening visit, four treatment visits and two follow up visits; a total of seven office visits to complete participation. (Screening visit and first treatment may be on same day if no biopsy is taken.) Biopsy patients will have a total of eight office visits to include an additional biopsy collection at 14 days post treatment #1 for enrollment completion.

### 5.6 Subject Enrollment

A subject is considered enrolled in the study at the time of the first treatment (Treatment #1) following confirmation of eligibility according to inclusion/exclusion criteria at the Screening Visit and again at Visit 2 (Treatment #1).

### 5.7 Subject Screen Failures

A subject who fails to meet eligibility criteria or discontinues from the study of their own volition before the first treatment will be considered a screen failure.

### 5.8 Subject Completion

The subject has completed the study when he/she completes Visit 7 (3-month follow-up). A subject who has missed visits or is missing study measurements will remain in the study. Subjects who require further follow-up for an adverse event (AE) or adverse device effect (ADE) will be followed according to Section 8.2. The same standard of care will be available for subjects who complete the study as for discontinued subjects (see Section 5.9) if such additional care is necessary because of the subjects' participation in the clinical investigation and where it differs from that normally expected for the medical condition in question.

### 5.9 Subject Discontinuation

A subject may discontinue from the study at any time without any penalty or loss of benefits to which the subject is otherwise entitled. An investigator may also discontinue a subject from the study without the subject's consent, if the investigator feels it is in the best medical interest of the subject. The date and reason for study withdrawal will be indicated on the study exit case report form. Every effort should be made to contact subjects lost to follow-up, and all such efforts should be documented in the subject's file.

If the subject withdraws from the study and also withdraws consent for disclosure of future information, no further evaluations will be performed, and no additional data will be collected. The Sponsor may retain and continue to use any data collected before such withdrawal of consent.

#### 5.9.1 Reason for Withdrawal or Termination

A study subject will be discontinued from participation in the study if:

- Any clinical adverse event (AE), laboratory abnormality, intercurrent illness, or other medical condition or situation occurs such that continued participation in the study would not be in the best interest of the subject.
- The subject meets any exclusion criteria (either newly developed or not previously recognized).

Subjects who are withdrawn will not be replaced.

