#### 5.4 Exclusion Criteria

Subjects will be excluded from the study if they meet any of the following criteria.

- 1. Pregnant, breastfeeding, or planning to become pregnant during the study.
- 2 History of any type of allergic reaction to lidocaine.
- 3. Recent and/or active localized or systemic infections.

- 4. Diagnosis/possibility of actinic keratosis, melasma, rosacea, or other significant skin conditions (e.g. skin cancer, active infections, cold sores, open wounds, rashes, burns, inflammation eczema, psoriasis).
- 5. Predisposition to keloid formation or excessive scarring.
- 6. Diagnosis of a condition that may compromise the immune system, such as: HIV, lupus, scleroderma, and/or systemic infections.
- 7. Known sensitivity to light or photosensitizing agents/medications are being taken.
- 8. Systemic steroids (e.g. prednisone, dexamethasone), which should be rigorously avoided prior to and throughout course of the treatment.
- 9. Use of retinoids less than 2 weeks prior to or during the study to completion.
- 10. Individuals undergoing Accutane™ treatment or drugs in a similar class.
- 11. Having skin that is still recovering from a cosmetic procedure: such as a chemical peel, or mechanical peel, or laser resurfacing within the previous 6 months.
- 12. Having had Botox injections, neurotoxin injections, or dermal fillers (such as collagen) within the past four months.
- 13. Sunburn and/or recent sun exposure on the treatment area in the last 2 weeks.
- 14. Subjects must agree to seek the advice of their medical doctor regarding any known or suspicious skin condition before laser treatment.
- 15. Any condition or situation that would prevent the subject from safely completing all protocol requirements for participation.
- 16. Subjects who are unable to communicate or cooperate with the investigator due to language problems, poor mental development, or impaired cerebral function.

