#### 5.9.2 Handling of Subject Withdrawal or Termination

If a subject voluntarily withdrawals, they will not be asked to continue the scheduled evaluations due to the short study duration. If subject is withdrawn from study because of adverse events they will be provided with the appropriate care under medical supervision.

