### 6.7 Study Completion

The Sponsor or its representative will notify the Investigator and/or the IRB, as applicable, to inform them when the study is complete. The study will be considered complete when all enrolled subjects either have completed study visits through Visit 7 (3-month follow up) or have been discontinued from the study prior to Visit 7 for any reason.

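### Section 5.9.1 takes a subject out of the whole study for newly meeting any exclusion criterion, even after the last laser session, so fully treated subjects can lose the 3-month primary score and the reported improvement becomes selective.

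*Combined protocol and SAP*

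**What the plan says.** Section 5.9.1 opens with "A study subject will be discontinued from participation in the study if" and lists two triggers. The first is a medical event or situation that makes staying in against the subject's best interest. The second has no such qualifier: "The subject meets any exclusion criteria (either newly developed or not previously recognized". The section then adds: "Subjects who are withdrawn will not be replaced".

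Some exclusion criteria in Section 5.4 describe states that can begin at any time, for example "Sunburn and/or recent sun exposure on the treatment area in the last 2 weeks". Others are active infection, cold sores, rashes, burns and photosensitizing medication. One runs expressly to the end of the study: "Use of retinoids less than 2 weeks prior to or during the study to completion".

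Three other sections bear on what happens next:

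- Section 5.8: "A subject who has missed visits or is missing study measurements will remain in the study".
- Section 5.9.2 says of voluntary withdrawals that "they will not be asked to continue the scheduled evaluations due to the short study duration", and of adverse-event withdrawals only that care is provided. It does not mention withdrawal for an exclusion criterion.
- Section 6.7 counts the study as complete once each enrolled subject has either finished through Visit 7 or "have been discontinued from the study prior to Visit 7 for any reason".

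Section 10.1 limits the ITT population to treated subjects with at least one post-baseline evaluation who have not been disqualified on other grounds. It bases percentages on subjects with non-missing data at the visit.

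**The concern.** The primary endpoint is the investigator's comparison of the baseline photograph with the photograph taken 3 months after the final treatment. By then the regimen is finished and only outcome assessment remains. As written, Section 5.9.1 still operates in that window, so a subject who had all four sessions and then has a sunburn or a cold sore falls under a mandatory discontinuation.

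The subjects removed may not resemble those who stay. Infection, rash, burns and inflammation are skin events, and a poorer skin result in those subjects is plausible, although the documents do not establish it. Leaving them out would then flatter the reported improvement. There is no control group in which the same loss would also occur.

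The rule is also likely to be applied unevenly. The Schedule of Events has eligibility review only at Visits 1 and 2, so later removals would depend on what comes to light through adverse event and medication review.

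**Working it through.** **1. Which results are exposed.** Timings are from Section 6.8: Visit 6 is 1 month and Visit 7 is 3 months after Treatment #4, each ± 7 days.

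| Discontinued | Investigator score, 1 month (secondary) | Investigator score, 3 months (primary) | GAIS and satisfaction |
|---|---|---|---|
| Between Treatment #4 and Visit 6 | lost | lost | lost |
| Between Visits 6 and 7 | kept | lost | lost |

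This assumes that discontinuation from participation ends the scheduled evaluations. Section 6.7 implies it; Section 5.9.2 does not say so for this type of withdrawal.

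**2. The plan's own size figures.** Section 10.1 gives more than 95% power at N = 25 and enrolls up to 30. The implied allowance is 30 − 25 = 5 subjects, or 5/30 = 16.7%, for losses of every kind. The power figure cannot be reproduced, because the mean change and variance taken from the earlier study are not given. Back-solving a one-sample t test (two-sided alpha 0.05, n = 25, power 0.95) gives a standardized effect d of about 0.75, or about 0.77 after allowing for the Wilcoxon relative efficiency of 3/π. Power is P(T > t₀.₉₇₅,ₙ₋₁), where T is noncentral t with noncentrality d√n. At that effect:

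| Evaluable n | 30 | 25 | 22 | 20 | 18 |
|---|---|---|---|---|---|
| Power | 97.8% | 95.0% | 91.9% | 89.0% | about 85% |

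Power therefore falls slowly as subjects are lost.

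**3. Effect on the test.** The investigator score runs from 0 to 4 and cannot be negative, and the usual signed rank test drops zeros. Six non-zero scores already give an exact two-sided p of 2/2⁶ = 0.031. In an illustrative set of ten 1s, ten 2s and five 0s, p = 0.00005, and adding five more 0s leaves p the same. Losing or keeping non-improvers hardly moves the p-value.

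**4. Effect on the estimate.** Let L of 30 be lost. The plan reports the rate r or mean m among the 30 − L observed. If the lost subjects count as not improved (score 0), these become r(30 − L)/30 and m(30 − L)/30. The observed rates of 100% and 80%, the mean of 1.5 and the values of L are assumptions.

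| L | Observed rate 100% becomes | Observed rate 80% becomes | Observed mean 1.50 becomes |
|---|---|---|---|
| 1 | 96.7% | 77.3% | 1.45 |
| 3 | 90.0% | 72.0% | 1.35 |
| 5 | 83.3% | 66.7% | 1.25 |

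These are lower bounds, not expected values. With L = 5 and 20 of 25 observed improving, the rate among all 30 lies between 20/30 = 66.7% and 25/30 = 83.3%, depending on the unseen outcomes. The width of that interval is 5/30 = 16.7 percentage points.

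**The case against.** The strongest defence is that the rule has a purpose. A retinoid, toxin, filler, sunburn or rash can change the photograph being scored, and an uncontrolled study cannot adjust for it. That stands, and it is why a sensitivity analysis is needed. It does not require that the outcome go uncollected.

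It can also be said that the rule was never meant to reach this far. Eligibility is checked only at Visits 1 and 2. The systemic steroid criterion is tied to the course of treatment, so a steroid taken after Treatment #4 is not clearly covered. The criterion on skin still recovering from resurfacing within 6 months could, taken literally, catch the study laser itself. This is fair as to intent, but the wording of Section 5.9.1 has no limit and no other section supplies one.

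A reader might draw four stronger conclusions that the documents do not support:

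- **Safety follow-up is lost.** Section 8.1.3 has all adverse events monitored until resolved or explained. Section 8.2 follows device-related and serious events still ongoing at the final visit and allows unscheduled visits. Only the scheduled Visit 6 and 7 scoring is at risk.
- **Evaluations are expressly stopped.** Section 5.9.2 is silent on this type of withdrawal; the loss is implied by Sections 5.9.1 and 6.7.
- **There is no analysis rule at all.** Section 10.1 does set a non-missing denominator for percentages. What is missing is a statement of whether these subjects remain in the ITT set and how they are counted.
- **The study becomes underpowered.** The share of subjects affected is not given. At assumed whole-study rates of 5%, 10%, 15% and 20%, the binomial chance of losing more than 5 of 30 is 0.3%, 7%, 29% and 57%. Those rates are not specific to the period after Treatment #4, and falling somewhat below 25 costs little power.

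**Conclusion.** The point holds as a gap in the withdrawal rule. Applied as written, Section 5.9.1 can remove fully treated subjects before the only visit that yields the primary endpoint, and Sections 5.8, 5.9.2, 6.7 and 10.1 do not repair this. The consequence is selection in the reported improvement rate and mean: each subject lost from 30 leaves 1/30, or 3.3 percentage points, of the all-treated rate undetermined, and 5 losses leave 16.7 points. This rests on reading discontinuation from participation as ending the scheduled visits. How many subjects would be affected, and whether their outcomes would be worse, cannot be determined from the documents. The change is worth making because it is cheap and because withdrawn subjects are not replaced.

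**What to change.** Reconcile Sections 5.9.1, 5.9.2, 6.7 and 10.1 so that ending laser sessions is separate from leaving the study. The rule for stopping laser treatment stays with the sponsor and is not altered by this point.

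- State that subjects who newly meet an exclusion criterion, including after Treatment #4, are still asked to attend Visits 6 and 7, where they agree, for photographs, investigator score and skin-response scoring, with GAIS and satisfaction at Visit 7.
- State that they stay in the ITT analysis, and define what disqualifies a subject from it.
- Flag subjects with an exposure or skin condition that could change the photograph (retinoid, toxin, filler, peel, sunburn, rash) and repeat the primary summary without them as a sensitivity analysis.

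The cost is protocol wording and one extra summary, since the visits are already scheduled. The downside is that some retained scores will be confounded; the sensitivity analysis shows how much that matters. The change is most useful before any such discontinuation occurs.

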#### 5.9.2 Handling of Subject Withdrawal or Termination

If a subject voluntarily withdrawals, they will not be asked to continue the scheduled evaluations due to the short study duration. If subject is withdrawn from study because of adverse events they will be provided with the appropriate care under medical supervision.

#### 6. STUDY PROCEDURES AND SCHEDULE:

#### 6.1 Informed Consent

The investigator must ensure that written informed consent to participate in the study and written authorization for use and disclosure of protected health information is obtained before including any individual as a subject in the study, and before conducting any study related assessments. The investigator must provide the prospective subject with sufficient opportunity to consider whether to participate and minimize the possibility of coercion or undue influence.

To participate in the study a subject must sign and date an IRB-approved consent document. The original, signed documents will be kept with these subjects' files and copies will be provided to the subjects. The informed consent process must be followed, and the subjects' participation in the study must be documented in the subjects' medical record/CRF.

### 6.2 Pre-Procedure

Study subjects will have verification of eligibility criteria, a brief general examination including medical history, vital signs and pre-procedure assessments as detailed below, completed within 30 days prior to undergoing the study procedure. Up to two urine pregnancy tests must be obtained prior to study procedure for females with childbearing potential (one at pre-procedure screening and one on the day of the procedure prior to the procedure if the pre-procedure screening and procedure are not performed on the same day).

The following pretreatment assessments will be performed:

- Standard 2D photographic images will be captured via the Canfield Scientific Inc, VISIA CA imaging system. The same standardized photography views (right, left, front facing) will be used throughout the study as documented in the image capture document developed for the study.
- Urine pregnancy test for females of childbearing potential; any premenopausal female capable of becoming pregnant. (Excluded: Non-childbearing potential, i.e. post-menopause, bilateral tubal ligation, oophorectomy, hysterectomy)
- Abbreviated general physical exam including medical history, vital signs, collection of subject's demographic information, Glogau photodamage assessment, Fitzpatrick skin type, Fitzpatrick Wrinkle and Elastosis Scale. (Appendixes A, B, C respectively)

Medications the subject is taking upon entry into the study should also be documented in the case report forms. Documentation should include medications that study subjects take on an elective basis in addition to prescribed medications.

After confirming fulfillment of all inclusion and exclusion criteria, the subject will be scheduled to undergo a CLEAR + BRILLIANT TOUCH® 1440-nm and 1927-nm combination wavelength treatment.

Patient Pre-treatment instructions:

[figure not shown]
- Skin types IV-VI: Begin Hydroquinone 8% QHS at discretion of treating physician, 2-3 weeks prior to first treatment. Hold while skin is healing between treatments, then restart QHS or as directed.
- Wash face with CeraVe® cleanser.
- Do not apply any topical facial products the morning of your treatment.
- Do not wear jewelry.
- Hair pulled back.
- Bring a hat to wear that shields from the sun.
- Bring on day of treatment the sponsor provided CeraVe® moisturizer and SPF to apply after treatment.

[figure not shown]

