# 1. STUDY SYNOPSIS

Name of Sponsor/Company	Bausch Health Americas, Inc.			
Name of Device	CLEAR + BRILLIANT TOUCH® diode laser 1440-nm and 1927-nm			
Title of Study	A Prospective, Single-Center Study Evaluating the Safety and Effectiveness of the CLEAR + BRILLIANT TOUCH® diode laser 1440-nm and 1927-nm Combination Wavelength Treatment.			
Number of Clinical Centers	Single Center			
Study Design	This is a prospective study of up to 30 subjects designed to assess the safety and effectiveness of a non-ablative fractional laser combination wavelength treatment for general resurfacing of photoaged skin. All study subjects will be treated on the whole face with the CLEAR + BRILLIANT TOUCH® 1440-nm and 1927-nm handpieces. Subjects will be treated with a consecutive series of four (4) treatments spaced 1 month apart, along with follow-up study visits at one (1) and three (3) months after final treatment.			
Study Population	To be eligible for the study, the subjects must have mild (I) to moderate (II) photoaging by Glogau Photodamage Scale, no more than fine wrinkles and mild elastosis by Fitzpatrick Wrinkle and Elastosis Scale (Class I-II, Score 1-6). Both males and females will be considered, between the ages 18 and 65 years and Fitzpatrick skin Types I-VI with 70% skin types I-III and 30% skin types IV-VI.  Number of subjects: Up to 30 subjects who meet all study inclusion/exclusion criteria will be considered for entry.			
Study Objective	The objective is to evaluate the effectiveness and safety of the CLEAR + BRILLIANT TOUCH® diode laser combination treatment of 1440-nm and 1927-nm.			
Study Endpoints	Primary Effectiveness Endpoint: improvement in the appearance of at least one measurement of photoaging damage (fine wrinkles, skin texture, dyschromia/pigment, skin radiance, pore size or overall appearance) by the investigator using the quartile improvement score comparing standard 2D baseline photograph captured via Canfield VISIA CA system and the 3 months post final treatment photograph. Reported percent change in improvement.			

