### 4. STUDY DESIGN AND ENDPOINTS

#### 4.1 Description of Study Design:

This is a prospective, non-randomized study of up to 30 subjects designed to assess the safety and effectiveness of a non-ablative fractional combination laser wavelength procedure for general resurfacing of photoaged skin. All study subjects will be treated on the whole face with the with the CLEAR + BRILLIANT TOUCH® diode laser 1927-nm & 1440-nm handpieces. Subjects will be treated with a consecutive series of four (4) treatments spaced 1-month apart, along with follow-up study visits at one (1) and three (3) months after final treatment. As primary and secondary effectiveness endpoints aim to evaluate improvement in photoaging damage post-treatment as compared to baseline following treatment with the FDA-cleared CLEAR + BRILLIANT TOUCH® System, no control group will be utilized.

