#### 5.3 Inclusion Criteria

Subjects must meet all the following inclusion criteria.

- 1. Male or female.
- 2. 18 to 65 years of age.
- 3. Written and oral informed consent must be obtained.
- 4. No more than Mild (I) to Moderate (II) classification on Glogau Photodamage Scale.
- 5. Fitzpatrick skin types I-VI.
- 6. Fitzpatrick wrinkle & elastosis scale class I-II, score 1-6 (fine wrinkles and mild elastosis).
- 7. Ability to read, understand and sign the informed consent form.
- 8. Agree not to take any new medications (unless prescribed by the study investigator) or undergo any other procedures that may potentially treat photodamaged skin (any other aesthetic treatments) during the study.

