#### **Post Care and Instructions:**

- 1. Wash face with CeraVe® gentle cleansing product only.
- 2. Do not use an abrasive cleanser or brush device to clean face.
- 3. Apply CeraVe® moisturizer minimum twice a day while skin is healing and then as needed.
- 4. SPF 30+ daily. (approved by investigator)

  Sun exposure before and during treatment can increase the risk of unwanted pigmentation. After treatment the skin is more sensitive to the sun, which can increase the risk of unwanted pigmentation and sunburn. Post-treatment individuals should plan to use a high SPF sunscreen on a regular basis whenever they are outside. Ideally, a dual UVA/UVB sunscreen should be applied containing both a physical sun block (either or both zinc oxide or titanium dioxide) with a sun protection factor of 30 or above. Applying sunscreen helps maintain good results. In general, it is recommended that direct sunlight is avoided and to wear sun-protective clothing (i.e. a wide-brimmed hat) when possible.
- 5. Schedule next appointment.
- 6. Review and dispense the Subject home diary for post treatment skin effects.
- 7. For patients on the 8% hydroquinone therapy (Skin types IV-VI) hold this application while skin is healing, then restart QHS or as directed.

Subjects will be asked to return to the study site for subsequent procedures and post treatment follow up.

Post procedure Standard 2D images will be captured via the Canfield Scientific Inc, VISIA CA imaging system during the follow-up visits.

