#### Visit 1 (Day 0-30)

Screening

A prospective subject is to be examined to determine if they qualify for entry into the study. This initial examination will include:

- Obtain written Informed Consent and photographic release
- Review Inclusion/Exclusion Criteria
- Record Medical History/Meds/Vital Signs
- Urine Pregnancy Test (if applicable): only one is necessary prior to start of treatments.
- Dispense CeraVe® Products
- Skin types IV-VI: Begin Hydroquinone 8% QHS at discretion of treating physician 2-3 weeks prior to first treatment. Hold while skin is healing, then restart QHS or as directed.
- Investigator Assessments: Glogau Photodamage, Fitzpatrick Skin Type and Wrinkle & Elastosis Scale
- Biopsy #1 of five patients (baseline)

Note: Screening and Baseline visits may occur on the same day for non biopsy patients.

#### Visit 2

Baseline/Treatment #1 (Screening/Baseline may be on same day)

This treatment visit will include:

- Photographs prior to treatment: wait at least 15 min indoors, 2D standard photography captured via Canfield VISIA CA.
- Urine Pregnancy Test (if applicable): only one is necessary prior to start of treatments.
- · Laser treatment to the face
- VAS Scale
- Post Treatment Skin effects (provider)
- Review for Adverse Events (provider)
- Subject Diary post treatment (7 days) given to patient.

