10.2.3 Minimization of Bias and Potential Confounding Factors
Blinded investigator photo evaluation is intended to minimize bias.

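### Hydroquinone 8% may be used by skin types IV-VI between the baseline and outcome photographs, and no planned analysis separates its effect from the laser's

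*Combined protocol and SAP*

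**What the plan says.** **Co-treatment.** Section 6.2 tells skin types IV-VI: "Begin Hydroquinone 8% QHS at discretion of treating physician, 2-3 weeks prior to first treatment". The Visit 1 list in section 6.8 repeats this and adds "Hold while skin is healing, then restart QHS or as directed". The post-care list in section 6.4 says "For patients on the 8% hydroquinone therapy (Skin types IV-VI) hold this application while skin is healing, then restart QHS or as directed". None of these places gives a stop date before the follow-up photographs. Inclusion criterion 8 (section 5.3) has subjects agree to take no new medication, but with the exception "unless prescribed by the study investigator".

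**Who is eligible.** The synopsis describes "Fitzpatrick skin Types I-VI with 70% skin types I-III and 30% skin types IV-VI", with up to 30 subjects. Section 5.3 admits types I-VI and sets no quota.

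**Design and outcome.** Section 4.1 states that "no control group will be utilized". The primary endpoint (section 4.2.1) is improvement in one or more of six categories, among them dyschromia/pigment and overall appearance. The treating investigator scores each from 0 to 4 against baseline photographs (section 7.2). The schedule in section 6.8 places the baseline photograph at Visit 2, before Treatment #1.

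**Analysis.** Sections 10.2.2 and the SAP table test the score against 0 with a Wilcoxon signed rank test in all subjects together. Skin type appears only in the baseline summary (section 10.1). Section 10.2.3, on bias and confounding, consists of one sentence: "Blinded investigator photo evaluation is intended to minimize bias".

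**The concern.** In an uncontrolled before/after study, whatever changes between the two photographs is credited to the study treatment. Here a second product may be applied nightly to the same face in that interval, in a subgroup defined by skin type, at the physician's discretion. Two of the six scored categories concern pigment or overall appearance.

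Blinding deals with what the rater expects. It does not help with two treatments whose joint result is in the same photograph. The remaining safeguard would be an analysis that looks at users and non-users separately, and section 10 has none. At stake is what a pigment result may be attributed to: the two-wavelength laser, or the laser plus hydroquinone in up to about 30% of subjects.

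**Working it through.** **1. Which use is confounded.** The baseline photograph is taken at Visit 2.
- Hydroquinone begun 2-3 weeks earlier: the lead-in effect is already partly in the baseline and so is partly absorbed. Only effect that accrues after Visit 2 counts towards improvement.
- Screening and Treatment #1 on the same day (sections 5.5 and 6.8 allow this for non-biopsy subjects): there is no lead-in under the study, and any use starts after baseline.
- Held and restarted between treatments: this use lies between the baseline and outcome photographs.

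Baseline status can therefore differ between users, and nothing in section 10 takes account of it.

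**2. How many subjects.** From the synopsis, 0.30 × 30 = 9 are eligible and 0.70 × 30 = 21 are not. Of the 25 in the power statement, 0.30 × 25 = 7.5 and 0.70 × 25 = 17.5, so 17-18 would be types I-III. Use is discretionary, so the number of users ranges from 0 to about 9.

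**3. Effect on the pooled mean.** If u of n subjects are users and hydroquinone adds an average of h points to a category, the pooled mean rises by (u/n) × h. With h = 1 (assumed), u = 9 and n = 30, this is 0.30 points; with u = 0 it is 0. The documents give no value for h in any category.

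**4. Illustrative worst case for the planned test.** The signed rank test drops zeros. If k users score above 0 and all others score 0, the exact two-sided p is 2 × 0.5^k:

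| k | p |
|---|---|
| 5 | 0.063 |
| 6 | 0.031 |
| 7 | 0.016 |
| 8 | 0.008 |
| 9 | 0.004 |

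Six of nine eligible subjects would suffice at alpha 0.05. This assumes no laser effect in anyone and a positive score in each of the k users.

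**5. The plan's power figure, and power without users.** Section 10.1 states more than 95% power with 25 subjects, based on overall appearance. It gives neither mean nor SD, so the figure cannot be reproduced. It is attainable: for a two-sided one-sample t test (noncentral t, n = 25, alpha 0.05), 95% power needs a standardized effect d of about 0.75. Taking d = 0.75 as an assumption:

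| n | What it represents | Power |
|---|---|---|
| 25 | planned evaluable | 95% |
| 21 | types I-III, no drop-out | 90% |
| 18 | types I-III, evaluable | 85% |
| 17 | types I-III, evaluable | 83% |

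The like-for-like comparison with 25 evaluable is 17-18 evaluable, not 21 enrolled. At d = 1.0, power at 17-18 would be 97-98%. The value 0.75 is derived from a statement about overall appearance; nothing in the documents shows that it applies to dyschromia.

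**The case against.** **The p-values do not measure hydroquinone.** Any six positive scores with the rest at 0, from whatever cause, give p = 0.031 on a 0-4 scale that has no category for worsening. This stands. The figure shows only how few subjects could carry the test.

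**A reader might infer that hydroquinone alone could meet the primary endpoint.** The documents do not support that. They give no size for its effect, section 10 defines no responder test for improvement in one or more categories, and the power statement concerns overall appearance.

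**A reader might also infer that any dyschromia claim should rest on non-users.** That would depart from the ITT population that section 10.1 makes primary. It would select subjects by a discretionary decision and, if most eligible subjects are users, confine the claim largely to skin types I-III. The documents do not call for it.

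**Use is already recorded.** Concomitant medications are collected at every visit except 2a. This stands and makes the fix cheap, but no analysis uses the record.

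**The exposure is limited.** Few subjects are eligible, melasma is excluded, photodamage is limited to Glogau I-II, and the lead-in is partly absorbed into baseline. These points reduce the likely size. They do not deal with use after baseline. Criterion 8 gives no reason for its restriction, so it cannot be cited as the protocol's own admission of confounding.

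**Conclusion.** The gap is real and moderate. In users, any effect of hydroquinone use that starts, continues or restarts after the Visit 2 photograph cannot be told apart from the laser's effect, and the plan as written credits it to the laser. Between 0 and about 9 of 30 subjects are affected. The upper figure rests on a split that stands only in the synopsis.

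The conclusion needs one assumption that the documents do not quantify: that hydroquinone may change a pigment or overall-appearance score. It does not depend on the p = 0.031 scenario, which is a worst case and not a prediction. It does not show that the trial would succeed without a laser effect, and it does not disturb the all-subject analysis as primary. What is missing is a reporting split, a sensitivity analysis, and careful attribution.

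**What to change.** Leave clinical use unchanged, and keep the all-subject ITT analysis as primary.

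1. From the concomitant medication record, capture hydroquinone start, hold, restart and stop dates, and their position relative to the baseline photograph.
2. In section 10.2, report investigator and blinded scores for dyschromia/pigment and overall appearance by hydroquinone use, and by skin types I-III versus IV-VI.
3. Pre-specify a sensitivity analysis of these scores that excludes users.
4. State in the plan that pigment results in users are attributed to the combined regimen, not to the laser alone.
5. Reconcile the passages on the 2-3 week lead-in (sections 6.2 and 6.8, Visit 1) with those that allow screening and Treatment #1 on the same day (sections 5.5 and 6.8).

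**Cost.** A few date fields and extra tables. If every type IV-VI subject is a user, the sensitivity analysis has about 21 enrolled or 17-18 evaluable subjects, with about 83-85% power at the assumed effect of 0.75, and 90% only with no drop-out. Because use is tied to skin type, the split describes the confounding but does not fully remove it.
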